9.1.3 Other study parameters

An inventory will be made of the following confounders gender, obstetrical and neonatological complications and education level of the parents according to the International Classification of Education. [25] We will assess the family history of allergies asthma and eczema to obtain information about possible confounding factors in our study groups. Also smoking and day-care visit will be questioned.

Table 2: Overview assessments

Study assessments			
Age group	Name assessment tool	Abbreviation	Outcome
Cognitive development			
2-3 years	Bayley scales of infant and toddler development third edition.	Bayley III	IQ score
4-6 years	Wechsler Preschool and Primary Scale of Intelligence third edition.	WPPSI III	IQ score
7-16 years	Wechsler Intelligence Scale for Children fifth edition	WISC V	IQ score
Motor development			
2-3 years	Bayley scales of infant and toddler development third edition	Bayley III	Motor test score
2-18 years	Neurologic Examination According to Touwen.	Touwen	Gross Motor Function Classification System
Quality of life			
5-7 years	Pediatric Quality of Life Inventory	PedsQoL	Health related quality of life score
8-12 years	Pediatric Quality of Life Inventory	PedsQoL	Health related quality of life score
Behaviour			
1.5-5 years	Child Behavior Checklist	CBCL	Behaviour test score
6-18 years	Child Behavior Checklist	CBCL	Behaviour test score
Course of infections			
2-18 years	Questionnaire based on 'Richtlijn diagnostiek naar onderliggende aandoeningen bij kinderen met recidiverende luchtweginfecties'		Indication for diagnostic evaluation by immunologist; Yes/No.

Table 2: Overview assessments

Study assessments			
Age group	Name assessment tool	Abbreviation	Outcome
Atopic constitution			
2-18 years	Questionnaire composed in collaboration with allergist ([name]).	(Parent reported)	Allergy
Severity of asthma and hay fever			
6-18 years	Control of allergic rhinitis and asthma test.	CARATkids	CARATkids score

Table 3: Definitions of outcome

Definitions of outcome		(1/3)
Outcome parameter	Definition	
Obstetric medical data		
Pregnancy induced hypertension	De novo hypertension (blood pressure above 140/90 mmHg) after gestational week 20.[26]	
Pre-eclampsia	De novo hypertension after gestational week 20 and new onset of one of the following; proteinuria (>300 mg/day), renal insufficiency, liver disease, neurological problems, hematological disturbances or fetal growth restriction. [26]	
Signs of bleeding in the fetus at ultrasound	For instance intraventricular hemorrhages or ventricular dilatation.	
Antenatal IVIg-treatment	Administration during pregnancy from 28 weeks gestational age or 16-18 weeks gestational age in high risk pregnancies according to the protocol of the LUMC.[27]	
Intra-uterine transfusions	Any platelet transfusions of the fetus during pregnancy.	
Treatment with corticosteroids	Maternal treatment with corticosteroids to prevent burden or worsening of alloantigen production.	
Mode parturition	Type of parturition (e.g. caesarean section and instrumental delivery).	
Gestational age at birth	Gestational age: completed weeks and additional days since the first day of the last menstruation period of the mother.	
Placenta weight	Weight of placenta after birth in grams.	
Neonatal data (part 1)		
Respiratory distress syndrome	Requiring mechanical ventilation and/or surfactant.	
Perinatal asphyxia	One of the following criteria; Apgar score < 7 and/or umbilical cord pH ≤ 7.0.	
Proven early onset neonatal sepsis	Positive blood culture within 72 hours postpartum and clinical suspicion of a neonatal sepsis.	
Retinopathy of prematurity	Staging according to ICROP [28]	
Neonatal morbidity	Scored positive if one of the following conditions were present: Respiratory distress syndrome, Perinatal asphyxia, Proven early onset neonatal sepsis, NEC, Retinopathy of prematurity.	

Definitions of outcome		(2/3)
Outcome parameter	Definition	
Neonatal data (part 2)		
Necrotizing enterocolitis	Stage 2 or higher [29]	
Intracranial hemorrhage	Any cranial hemorrhage	
Intraventricular hemorrhage	Grading according to Volpe [30]	
Cystic periventricular leukomalacia	Grade 2 or higher [31]	
Ventricular dilatation	Above 97th percentile [32]	
Porencephalic or parenchymal cysts	Presence of porencephalic or parenchymal cysts. Porencephalic cyst: focal area of encephalomalacia that communicates with the ventricular system and/or the subarachnoid space. Parenchymal cyst: smooth rounded borders and minimal-to-no surrounding signal intensity abnormality.	
Convulsions	Any paroxysmal, repetitive or stereotypical events interpreted as neonatal convulsions by a pediatrician.	
Signs of bleeding		
Intracerebral bleeding	Any bleeding in the cerebral cavity.	
Organ bleeding	Bleeding in any organ located in the thorax or abdomen.	
Postpone bleeding	Postpone bleeding that was noted as sign of bleeding by the caretaker.	
Skin manifestations	Petechiae, purpura or hematoma diagnosed by the caretaker at neonatal period (gynecologist, pediatrician or midwife).	
Neonatal IVIG treatment	Any administration of IVIG after birth.	
Platelet transfusion	Any platelet transfusion.	
Neurodevelopmental impairment		
Cerebral Palsy	Spastic bilateral, spastic unilateral or mixed Classification by European CP Network [19].	
Impaired cognitive or motor development	Score < 70 (2 SD below the mean) as assessed by Bayley Scales of Infant and Toddler Development version 3 (BSID III) [16]	
Bilateral blindness	Blind or partially sighted.	
Bilateral deafness	Needing hearing aids.	

Definitions of outcome		(3/3)
Outcome parameter	Definition	
Secondary outcomes		
Abnormal course or incidence of infections	Need to refer to an immunologist or the need to perform diagnostics based on history taking according to the Dutch guidelines. [23]	
Prevalence of allergies	Parent reported allergy.	
Patient reported anaphylaxis	Serious allergic reaction, requiring urgent medical treatment with epinephrine.	
Poor control of allergic rhinitis	CARAT score of upper airways < 8.[22, 33]	
Poor control of asthma	CARAT score of lower airways < 16.[22, 33]	
Prevalence of eczema	Parent reported eczema.	
Demographic characteristics		
Ethnic origin of the parents	Ethnic origin of mother and father.	
Educational level of the parents	Highest level of graduation of the parents.	
Smoking	Any person living in the household of the child smoking one or more cigarettes a day.	
Day-care visit	When child is in day care at least one day a week.	
Family history (first degree) of allergy, asthma or eczema	Positive when 1 st degree of family members receive daily treatment for asthma or eczema. Or when a family member wears an epinephrine pencil because of a severe allergy.	

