3.2 Secondary Objective(s)

In both groups we will assess the incidence of neurodevelopmental impairment (NDI). NDI is a composite outcome including cerebral palsy (GMFCS \geq II), cognitive or motor test score of less than 70, hearing loss requiring amplification or visual impairment (legally certifiable as blind or partially sighted). Other secondary outcomes will be HRQoL and behavioral problem score. In both cohorts we will assess academic performance by evaluation of test scores on three domains; arithmetic and spelling performance and reading comprehension. [11-13]

We will also focus on potential long-term side effects of IVIg treatment and determine the prevalence of allergies, eczema, asthma and the course of infections.

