4. STUDY DESIGN

We will perform an observational cohort study. The long-term neurodevelopmental outcome of children affected by FNAIT will be evaluated. All children born between 2002 and 2017 and diagnosed with FNAIT are eligible for follow-up assessment and will be invited for an assessment at our outpatient clinic. The FNAIT survivors will be collected in two cohorts; cohort 1 will consist of FNAIT survivors without antenatal treatment, cohort 2 will consist of FNAIT survivors that were antenatally anticipated and therefore IVIg treatment to the mother was given. A summary of our study design is presented in Figure 1.

Enrollment in our study will take place via the LUMC and Stichting Sanquin Bloedvoorziening. The LUMC is national referral center for intrauterine therapy and Sanquin is national reference laboratory to diagnose FNAIT. Retrospectively FNAIT cases will be collected and asked for permission directly or via referring specialist according to the procedures described in paragraph 12.2.

After informed consent, child cognitive functioning will be assessed with a formal psychological test of cognitive functioning described in table 2, chapter 9. According to age, the parents will complete a standardized behavioral and HRQoL questionnaire. Academic performance will be assessed by collecting the most recent CITO test scores from the Dutch Pupil monitoring system developed by the National Institute for Educational Measurement [14]. Assessment of the prevalence of possible late effects of IVIg on the immune system will be assessed by questionnaires about the prevalence of allergies, asthma, eczema and course of infections by questionnaires. Parents and children, when 12 years old or older, are asked for consent to request the medical letters from the maternity or neonatology ward to obtain perinatal and neonatal data.

Figure 1: Study design

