5.2 Inclusion criteria

In order to be eligible to participate in this study, a subject must meet all of the following criteria:

- Children diagnosed with FNAIT during pregnancy or postnatal, at moment of inclusion 2 to 16 years of age.
- Children living in the Netherlands.
- Parents or guardian aged ≥ 18 years old, with parental authority.
- Written informed consent form both parents with, form being approved by Ethic Committee.

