5.4 Sample size calculation

Of note, performing sample size calculations in the context of this rare disease is difficult since literature is scarce and heterogeneous.

We performed two different sample size calculations for the two cohorts.

Cohort 1: Using the literature to date we estimated that the IQ score of FNAIT survivors without antenatal treatment is lower, that is 92 versus average (100) in the normal population. To show a difference in IQ score between FNAIT survivors without IVIg treatment compared to a fixed average of 100, we performed a sample size calculation for a one-sample t-test. We calculated that a minimum group size of 39 was needed to show a mean difference of 7 IQ points with a power of 0.8 and a significance of 0.05. We assume a standard deviation (SD) of 15 for the IQ score.

Cohort 2: In the FNAIT survivors with antenatal treatment we expect no difference in IQ score between cases and the national average. To show that there is no difference IQ score in anticipated IVIg treatment compared to the Dutch average we perform a non-inferiority calculation by a one-sample t-test. In this case we need a sample size of 39 children with a non-inferiority margin of 7 IQ points, with a power of 0.8 and a significance level of 0.025. We assume a standard deviation (SD) of 15 for the IQ score.

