9.1.2 Secondary study parameters/endpoints

NDI is a composite outcome of:

- Cerebral palsy \geq grade II according to Gross Motor Classification System (GMFCS) [19]
- Impaired cognitive, language and/or motor development (test scores <70)
- Bilateral blindness and/or bilateral deafness
- Bilateral deafness requiring amplification

The Health Related Quality of life will be assessed with PedsQL and behavioral problem score will be assessed using the Child Behavior Checklist [20, 21].

Academic performance will be evaluated by obtaining test scores from the Dutch Pupil monitoring system. [14] The latest test scores from primary school will be requested. If children are in high school grades from grade 6 in primary school will be used in our evaluation to obtain uniform test scores. Three academic domains will be assessed; arithmetic and spelling performance and measurements on reading comprehension. Of these three domains the following scores will be obtained from the monitoring system; the raw test scores, standardized test scores and the level of the child.

To assess long-term effects of maternal IVIg treatment on the immune system of the child we will assess two outcome parameters:

- The prevalence of allergies, asthma and eczema will be evaluated by a questionnaire composed in collaboration with an allergist. The severity and control of the allergic rhinitis will be assessed by the CARATkids questionnaire [22].

- The prevalence of children with an abnormal incidence or frequency of infections will be assessed by a questionnaire based on the guideline; 'Richtlijn diagnostiek naar onderliggende aandoeningen bij kinderen met recidiverende luchtweginfecties' [23] and the 10 warning signs of PI of the Jeffrey Model Foundation. [24]

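### Table 2 schedules the quality-of-life questionnaire only for ages 5 to 12, although children aged 2 to 16 are eligible and the HRQoL outcome carries no age limit

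*Combined protocol and SAP*

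**What the plan says.** - **Eligibility (5.2).** Children must be "at moment of inclusion 2 to 16 years of age".
- **Objective (3.2).** "Other secondary outcomes will be HRQoL and behavioral problem score". The paragraph concerns both cohorts and names no age group to be left out.
- **Endpoint (9.1.2).** "The Health Related Quality of life will be assessed with PedsQL", again with no age limit. The Summary likewise has parents complete an HRQoL form for their children without qualification.
- **Design (4).** "According to age, the parents will complete a standardized behavioral and HRQoL questionnaire".
- **Schedule (Table 2, in 9.1.3).** The quality-of-life block has two rows, 5-7 years and 8-12 years, both for the "Pediatric Quality of Life Inventory". There is no row for ages 2-4 or 13-16.
- **Procedures (9.3).** The HRQoL form goes to the family's home before one outpatient assessment and is brought to that visit.
- **Analysis (11).** No analysis set, comparator or model is given for HRQoL.

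**The concern.** The text that defines the outcome and the table that schedules it do not describe the same children. A site working from the table would send no HRQoL form to a 3-year-old or a 14-year-old. A reader of the objectives would expect a score from both.

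The loss could not be repaired later. The plan has a single assessment per child, so a questionnaire not sent out for it cannot be recovered in the analysis. HRQoL in preschool children and adolescents could then not be described in either cohort. Unless the report states the restriction, a figure for ages 5-12 could be read as the HRQoL of the whole cohort.

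**Working it through.** The plan states no figure for HRQoL coverage, so there is none to reproduce. The check is a count of whole age-years.

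**Inputs**
- Eligible ages (5.2): 2 to 16, which is 16 − 2 + 1 = 15 age-years.
- HRQoL rows (Table 2): 5-7 (3 age-years) and 8-12 (5 age-years).

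**Coverage**
- Covered: 3 + 5 = 8 age-years.
- Uncovered: 15 − 8 = 7 age-years, namely 2, 3, 4 and 13, 14, 15, 16.
- Share of age-years uncovered: 7/15 = 46.7%.

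**The same count for other rows of Table 2**

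| Domain | Age rows | Eligible age-years uncovered |
|---|---|---|
| Cognition | 2-3, 4-6, 7-16 | 0 |
| Behaviour | 1.5-5, 6-18 | 0 |
| Infections; allergy questionnaire | 2-18 | 0 |
| HRQoL | 5-7, 8-12 | 7 |

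**Sensitivity to the age range.** The Summary's statement of burden mentions follow-up at 7 to 17 years. On a range of 2 to 17 the gap would be 8 of 16 age-years (50%).

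**From age-years to children (illustration only).** The documents give no age distribution, so the share *s* of children outside 5-12 has to be assumed. The base of 39 is borrowed from section 5.4, where it is the minimum group size for the IQ comparison. It is not an HRQoL target, and it is not a cap, since all eligible children are invited. Children without a score per 39 = 39 × *s*:
- *s* = 0.30: 39 × 0.30 = 11.7, about 12.
- *s* = 7/15 (ages evenly spread): 39 × 7/15 = 18.2, about 18.
- *s* = 0.60: 39 × 0.60 = 23.4, about 23.

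**Is the table merely damaged?** Rows lost when the PDF was read cannot be fully excluded. However, the quality-of-life block runs from its heading through two complete rows straight to the behaviour heading. The page split in Table 2 comes later, before the atopy rows. The block reads as complete.

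**The case against.** The strongest reply is that the phrase about age in section 4 already limits HRQoL to children for whom a form is listed. It can be read that way. But the same sentence covers the behavioural questionnaire, which has a form for every eligible age, so the more natural reading is that age decides which version is used. Even on the narrower reading, neither 3.2 nor 9.1.2 states the restriction, and section 11 defines no analysis set to match it.

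A second reply is that partial age coverage recurs in this plan. The Bayley motor score is listed at 2-3 years only, CARATkids at 6-18, and academic scores come from primary school. That is fair, and the full coverage of behaviour does not by itself prove that the HRQoL rows are an error. The cases differ in part: the Touwen examination covers motor function at 2-18, and parent-reported allergy is also collected at 2-18. HRQoL has no second measure at the uncovered ages.

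Three stronger readings are tempting, and the documents do not support them:
- *That the protocol deliberately leaves these ages unmeasured.* Table 2 is an overview and the endpoint text is unrestricted. Either two bands were left out or a restriction was left unstated; the documents do not show which.
- *That the gap distorts a comparison between the cohorts because they differ in age.* No age data are given for either cohort, and section 11 specifies no between-cohort HRQoL comparison.
- *That about half of the children lose their score, with a known loss of precision.* The 7 of 15 is a share of age-years, not of children, and no HRQoL analysis is specified whose precision could be calculated.

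**Conclusion.** The point holds as an inconsistency between Table 2 and sections 3.2, 4, 5.2 and 9.1.2, with a practical consequence. If the table is followed, 7 of 15 eligible age-years have no HRQoL instrument and the result applies to ages 5-12 only. That count is exact for the age range in 5.2. It assumes only that the quality-of-life block of Table 2 is complete as it reads.

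The number of children affected is unknown. The range of about 12 to 23 per 39 rests on an assumed 30% to 60% outside ages 5-12, and the value of about 18 on an even spread of ages.

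This should be corrected because it concerns a named secondary outcome collected once. It does not touch the primary outcome, since the cognitive tests cover every age from 2 to 16.

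**What to change.** Settle one of two options before enrolment.

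1. **Extend the schedule.** Add HRQoL rows to Table 2 for ages 2-4 and 13-16, using age versions of the same inventory. The documents do not show whether such versions and usable reference values are available, so the sponsor must confirm this first.
2. **Restrict the outcome.** If option 1 is not possible, state in 3.2 and 9.1.2 that HRQoL is assessed at ages 5-12 only, and report the number assessed in each cohort beside the result.

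Option 1 costs two table rows and a questionnaire for those ages in the packet that already goes to the home; no visit is added. Option 2 costs a sentence in each of two sections and a reported count. If the plan is already approved, either change must be notified to the ethics committee as an amendment (13.3).

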Methods: Neurodevelopmental evaluation of the children will be performed, at a minimum age of 24 months. This includes an assessment of neurologic, motor and cognitive development using standardized psychometric tests appropriate for age and parent-report questionnaires on Health Related Quality of Life (HRQoL) and behavioral functioning. Academic trajectories of FNAIT children will be assessed by collecting test scores from the Dutch pupil monitoring system. We will assess allergies and the course of infections by questionnaires.

Main study parameters/endpoints: The primary outcome is cognitive development i.e., cognitive test score or Intelligence Quotient (IQ). Secondary outcome is neurodevelopmental impairment (NDI); a composite outcome including cerebral palsy Gross Motor Functioning

Classification System (GMFCS) \geq II, cognitive and/or motor test score of less than 70 (-2 SD), hearing loss requiring amplification or visual impairment (legally certifiable as blind or partially sighted). Other secondary outcome parameters are HRQoL and behavioral functioning and the academic performance. The course and incidence of infections and allergies will be assessed.

Nature and extent of the burden and risks associated with participation, benefit and group relatedness

The burden of neurodevelopmental assessment tests is minimal (e.g. 120 minutes at 2 to 6 years and 150 minutes at 7 to 17 years follow-up). Neurodevelopmental assessment is generally experienced as enjoyable for children. Parents will complete a HRQoL- and a behavioral questionnaire for their children. Academic performance will be evaluated by scores that were obtained at school. Participation does not result in any direct benefit.

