3.3 Other study parameters

We will gather the data about the following data of our cases; age and sex of the child, obstetric medical data and neonatal characteristics and morbidity of the study population. Parents will be asked to complete a questionnaire to assess the highest level of education of the parents. We use this data to describe our study population and correct for potential confounding of these factors on neurodevelopmental outcome as described in chapter 11. Study parameters are summarized in Table 1, a list of definitions can be found in Table 3.

Possible confounding factors for allergies are the family history for asthma, allergies or eczema. For evaluation of the infections it is important to assess smoking at home and day-care visit as possible confounding factors.

Table 1: Study parameters

Study parameters		
Obstetric data	Maternal characteristics	Age mother at delivery Obstetric history Medication usage during pregnancy
	Pregnancy characteristics	Gravidity/Parity Pregnancy induced hypertension Pre-eclampsia Signs of bleeding in the fetus at ultrasound
	FNAIT related therapy	IVIg treatment Intra-uterine transfusions Treatment with corticosteroids
	Labour characteristics	Mode parturition Gestational age at delivery
	Placental features	Placenta weight
Neonatal data	Birth data	Gestational age at birth Birthweight Apgar score
	Severe neonatal morbidity	Respiratory distress syndrome Perinatal asphyxia Proven early onset neonatal sepsis Retinopathy of prematurity Necrotizing enterocolitis
	Neonatal neurologic sequelae	Intracranial haemorrhage Cystic periventricular leukomalacia Ventricular dilatation Porencephalic or parenchymal cysts Convulsions Any cerebral lesions associated with adverse neurologic outcome
	Signs of bleeding	Skin manifestations Intracerebral bleeding Organ bleeding Increased bleeding tendency, reported by the caregiver
	Therapy	Platelet transfusions IVIg treatment

Table 1: Study parameters

[figure not shown]
Study parameters		
Laboratory data	HPA	HPA incompatibility HPA genotyping Anti-HPA-titre Platelet count Directly after birth Nadir Other Presence of HLA class I antibodies

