9. METHODS

9.1 Study parameters/endpoints

9.1.1 Main study parameter/endpoint

To determine the cognitive and motor development score in children diagnosed with FNAIT without and with antenatal treatment. This will be evaluated using formal neurologic examination [15] and Bayley scales of Infant and Toddler Development third edition (Bayley III) at 2-3 years,[16] Wechsler Preschool and Primary Scale of Intelligence third edition (WPPSI III) at 4 to 6 years,[17] and Wechsler Intelligence Scale for Children fifth edition (WISC V) at 7 to 16 years [18].

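### Table 3 ties the cognitive and motor part of NDI to the Bayley-III, a test given only at 2-3 years, and the plan's NDI lists also differ on hearing, vision and language

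*Combined protocol and SAP*

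**What the plan says.** NDI incidence is a secondary objective in both cohorts (section 3.2). Section 3.3 states that "a list of definitions can be found in Table 3". Under the NDI heading of Table 3 (section 9.1.3), impaired cognitive or motor development is "Score < 70 (2 SD below the mean) as assessed by Bayley Scales of Infant and Toddler Development version 3 (BSID III").

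Section 9.1.1 assigns the cognitive tests by age, and Table 2 repeats the scheme:

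- "Bayley scales of Infant and Toddler Development third edition (Bayley III) at 2-3 years"
- "Wechsler Preschool and Primary Scale of Intelligence third edition (WPPSI III) at 4 to 6 years"
- "Wechsler Intelligence Scale for Children fifth edition (WISC V) at 7 to 16 years"

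Three other places define the composite without restricting it to a test:

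- Summary: "cognitive and/or motor test score of less than 70 (-2 SD), hearing loss requiring amplification or visual impairment"
- Section 3.2: "cognitive or motor test score of less than 70, hearing loss requiring amplification or visual impairment (legally certifiable as blind or partially sighted")
- Section 9.1.2: "Impaired cognitive, language and/or motor development (test scores <70")

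Table 1 also lists NDI items, without thresholds. They include bilateral blindness, bilateral deafness and an item on communication. No section says which list governs, and section 11 does not mention NDI.

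**The concern.** The section that readers are told to consult for definitions names one test, and most eligible ages do not take it. A 10-year-old with a WISC-V IQ of 65 has NDI under the Summary, 3.2 and 9.1.2, but does not meet the cognitive criterion under Table 3. A child with one-sided hearing loss who needs amplification meets the Summary and 3.2, but not 9.1.2 or Table 3.

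At stake is the reported incidence of a named secondary outcome. Expected counts are a few children per cohort, so reclassifying one or two changes the percentage visibly. As written, the choice between definitions could be made after the data are seen.

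**Working it through.** **The lists side by side**

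| Item | Summary and 3.2 | 9.1.2 | Table 3 | Table 1 |
|---|---|---|---|---|
| Cognitive/motor | <70, no test named | <70, no test named | <70 on Bayley-III | listed, no threshold |
| Language | absent | <70 | absent | communication item, no threshold |
| Hearing | needs amplification; laterality not stated | bilateral, listed once without and once with amplification | bilateral, hearing aids | bilateral, no threshold |
| Vision | legally certifiable, includes partial sight; laterality not stated | bilateral blindness | bilateral, includes partial sight | bilateral blindness |
| Cerebral palsy (CP) | GMFCS ≥ II | GMFCS ≥ II | type only | listed, no threshold |

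Eligibility is 2 to 16 years (5.2), or 15 single-year ages. Two of them (2 and 3) take the Bayley-III, so 13 of 15 have no test that can meet Table 3's row as written.

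**The plan's own figures.** The documents give no NDI rate, so there is none to reproduce. The cut-off is consistent: 100 − 2 × 15 = 70. The 39 in 5.4 also reproduces: a one-sample t-test for 7 points with SD 15 has power 0.811 at n = 39, at two-sided 0.05 or one-sided 0.025.

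**Cognitive criterion only.** From 5.4: SD 15, means 92 and 100, n = 39. Assumed: normal scores, and a share s of children aged 2-3 equal to 2/15 if ages are even. All 39 stay in the denominator.

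- p = Φ((70 − mean)/15).
- Mean 92: Φ(−1.467) = 0.0712, and 39 × 0.0712 = 2.78 children. Under Table 3, 2.78 × 2/15 = 0.37.
- Mean 100: Φ(−2) = 0.0228, and 39 × 0.0228 = 0.89. Under Table 3, 0.89 × 2/15 = 0.12.
- Mean 93 (the 7-point difference also used in 5.4): p = 0.0626, or 2.44 children; under Table 3, 0.33.
- If s is anywhere from 4% to 30%, the Table 3 count at mean 92 is 0.11 to 0.83.

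**Total NDI.** Let q be the rate of the CP and sensory components, assumed 2-10% and the same under both wordings, with s from 4% to 30%.

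- Independent components: 1 − (1 − p)(1 − q) with no test restriction, against 1 − (1 − ps)(1 − q) under Table 3. At mean 92 with q = 0.02 and s = 0.04 this is 0.0898 against 0.0228, so 25% of cases are kept. With q = 0.10 and s = 0.30 it is 0.1641 against 0.1192, so 73% are kept. The loss is 2.61 to 1.75 children. At mean 100, 49-88% are kept and 0.83 to 0.56 children are lost.
- Maximal overlap: max(p, q) against q + (p − min(p, q))s. At mean 92 with q = 0.02 and s = 0.04 this is 0.0712 against 0.0220, so 31% are kept. With q = 0.10 both are 0.10 and nothing is lost. At mean 100, 88-100% are kept.

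**Motor score.** Table 2 plans a motor test score only at 2-3 years. From age 4 it has only the neurological examination, which yields the GMFCS level. On every reading, a motor score below 70 can therefore arise only at 2-3 years.

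The hearing, vision and language differences are not quantified here.

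**The case against.** The strongest reply is that nobody would apply the Bayley-only row. Three of the four definitions name no test, the Summary promises tests suited to age, and 9.1.1 and Table 2 assign an IQ measure at every age. The row then reads as an unfinished citation. That reading is the likely one, and a reader should not infer that the investigators mean to ignore low IQ from age 4 or that NDI will be under-reported. What stands is that the text says otherwise in the place named for definitions, and no passage overrides it.

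Four stronger readings are not supported:

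- That most NDI cases would be lost. The age mix, the rates of the other components and their overlap are all assumed, and the loss can be nil.
- That the language item in 9.1.2 raises incidence. Table 2 plans no language score at any age, so the documents show no data on which it would change a count.
- That laterality differs as clearly for vision as for hearing. Legal certification may already imply both eyes. The clearer difference for vision is the threshold, blindness alone against partial sight included.
- That Table 3 drops the GMFCS threshold. Its CP row may define only the diagnosis, with the threshold applied in the composite.

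It is also fair to say that NDI is secondary and has no planned test. That limits the weight of the point but does not remove the conflict.

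**Conclusion.** The point holds as a conflict of written definitions. Following Table 3 literally would omit IQ below 70 at ages 4-16 that the other three definitions count: about 2.8 against 0.4 children at mean 92, and 0.9 against 0.1 at mean 100. Those figures rest on normal scores, SD 15, 39 children in the denominator and an even age spread. The last is an assumption, because the documents give no age distribution. The hearing conflict (laterality, and the two deafness bullets in 9.1.2) and the vision threshold need an actual decision, because inferring the right cognitive test does not settle them.

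A reader might extend this to the main result. The documents do not support that: the primary outcome is the IQ score itself, and neither its analysis nor the 39 in 5.4 uses NDI. The point should be fixed, but it threatens only the reported NDI incidence.

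**What to change.** In Table 3 write: *cognitive score <70 on the age-appropriate test in Table 2 (Bayley-III, WPPSI-III or WISC-V); motor score <70 on the Bayley-III, at 2-3 years only*.

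- Use one identical NDI list in the Summary, 3.2, Table 1, 9.1.2 and Table 3. It should have CP at GMFCS ≥ II, the criteria above, and one hearing and one vision wording, each stating laterality and threshold. Merge the two deafness bullets in 9.1.2.
- Delete the language item from 9.1.2 and align or remove the communication item in Table 1, unless a language score with its test and ages is added to Table 2.
- State that from age 4 motor impairment enters NDI only through CP with GMFCS ≥ II.
- Settle this before NDI is tabulated. A further tabulation without the motor score, comparable across ages, is optional.

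The cost is text edits in five places and no new testing, unless a language score is added. Motor impairment without CP stays uncounted from age 4. The plan already has that limit, and the edit only makes it explicit.
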